1.2 Rationale

Biochemical recurrence (BCR) in hormone-naïve prostate cancer is characterized by a rising prostate-specific antigen (PSA) after curative therapy, radical prostatectomy, or radiotherapy without recurrent or metastatic cancer on conventional imaging studies. It occurs in approximately 20-40% of post-prostatectomy patients and 30-50% of post-radiation patients within 10 years (Artibani et al. 2018). While many patients with BCR do well clinically for years, proper adequate treatment of BCR is important as BCR precedes the appearance of clinical metastasis by 8 years after radical prostatectomy (RP) and by 7 years after primary definitive radiotherapy (RT) (Artibani et al. 2018). Various management options are acceptable for prostate cancer with BCR, including observation, intermittent or continuous use of androgen deprivation therapy (ADT), non-steroidal anti androgen (NSAA) therapy, and salvage radiotherapy or radical prostatectomy with pelvic lymph node dissection, depending on the prior definitive therapy (National Comprehensive Cancer Network 2021).

Androgen deprivation therapy (ADT) currently constitutes the current first line systemic treatment for prostate cancer, resulting in marked suppression of serum testosterone levels and associated loss of libido and sexual function (DiBlasio et al. 2008). ADT also has well documented metabolic adverse effects including decreased bone mineral density, loss of muscle mass, increased lipid levels, and insulin resistance leading to a higher risk of diabetes and contributing to an increased risk of cardiovascular disease (Jespersen et al. 2014, Taylor et al. 2009). Attempts to reduce the morbidity of systemic prostate cancer treatments with less adverse effects have largely focused on non-testosterone lowering strategies using first generation NSAA monotherapies, an approach that is supported by EAU Guidelines on Prostate cancer (Mottet et al. 2020) and largely based on benefits in health-related quality of life (HRQoL) and tolerability. In contrast to ADT, NSAAs are associated with increased bone mineral density and reduced risks of fat accumulation, hyperglycemia, anemia, fatigue, loss of libido, and vasomotor flushing. NCCN guidelines for prostate cancer (National Comprehensive Cancer Network 2021) do not recommend the use of NSAA monotherapies due to lack of adequate follow up.

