To evaluate the impact of darolutamide monotheray on serum testosterone level over a 12-week intervention period	Change in serum testosterone level from baseline to week 12
Secondary	
To evaluate the impact of darolutamide monotherapy on serum testosterone level over the course of a 52-week intervention period	Change in serum testosterone level from baseline at week 24 and 52
Assess PSA response rate	Serum PSA Week 4, 12, 24, 36, 52
To assess safety of darolutamide monotherapy in patients with hormone-naïve prostate cancer with BCR	AE assessments using NCI CTCAE (v.5.0)

Abbreviations: BCR-Biochemical Recurrence, NCI CTCAE-National Cancer Institute Common Terminology Criteria for Adverse Events, PSA Prostate Specific Antigen.

Page: 16 of 86

Table 1-2: Randomized Phase Objectives and Endpoints

Objectives	Endpoints					
Primary						
To compare the effects of treatment with darolutamide vs. enzalutamide monotherapy on serum testosterone level over a 12-week intervention period	Change in serum testosterone level from baseline to week 12					
Secondary						
To compare the effect of darolutamide vs. enzalutamide monotherapy on serum testosterone level over the course of a 52-week intervention period	Change in serum testosterone level from baseline at week 24 and 52					
Measure changes in markers of endocrine function related to sex hormones	Assess changes in the blood levels of sex hormones (DHT, DHEA, SHBG, LH, FSH, Androstenedione, Prolactin, Estradiol)					
Measure changes in markers of components of fat and glucose metabolism	Assess changes blood levels of Total cholesterol, High-density and low-density lipoproteins, Triglycerides, Hemoglobin A1C, Fasting insulin, Fasting glucose, Fat body mass, Lean body mass					
Assess PSA response rate	Serum PSA Week 4, 12, 24, 36, 52					
To assess safety and QoL of darolutamide vs. enzalutamide monotherapy in patients with hormone-naïve prostate cancer with BCR	AE assessments using NCI CTCAE (v.5.0) and FACT-P					
Exploratory						
Evaluate changes in Bone turnover	Markers of bone turnover: BSAP, CTX, DEXA scan					
Physical function*	Subjective physical function: Godin – 4 questions, PROMIS Fatigue – 8 questions, PROMIS Physical – 6 questions, Self- Efficacy – 9 questions					

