^a Radiological tumor assessments will be conducted only at screening to exclude presence of visceral metastases, and because these are not considered standard of care, will only be done at other times based on treating physician discretion and based on PSA progression. Investigators are encouraged to provide the results of PSMA-PET CT scans in the eCRF if performed (optional at baseline or during the study).

If patient treatment discontinued BEFORE completing the full 52-week treatment, please refer to the Active Follow Up Period SoA Table 1-5.

Bayer will provide questionnaires wherever validated version is available in the said language.

Abbreviations: A1C (hemoglobin) Glycated, AE adverse event, ALT Alanine aminotransferase, AST Aspartate aminotransferase, BSAP bone-specific alkaline phosphatase, CT computerized tomography, CTX C-terminal telopeptide, DEXA dual energy x-ray absorptiometry, DHEA dehydroepiandrosterone, DHT dihydrotestosterone, ECG Electrocardiogram, ECOG Eastern Cooperative Oncology Group, EOT end of treatment, FACT-P Functional Assessment of Cancer Therapy – Prostate Cancer, FSH-follicle-stimulating hormone, INR international normalized ratio, LH-luteinizing hormone, MRI magnetic resonance imaging, PC prostate cancer, PSA Prostate-specific antigen, PSMA-PET Prostate-specific membrane antigen positron emission tomography, PT prothrombin time, PTT partial thromboplastin time, SAE serious adverse event, SHBG sex hormone-binding globulin, SOC standard of care.

^b Safety assessments should be continued as per SOC at time of progression. After the 30-day short term follow-up period, only SAEs that are considered related to study intervention or study participation, with concomitant medications used to treat the event, should be reported by the investigator. Documentation of progression should be provided to the Sponsor (in CRF).

^c During the treatment period and up to 30 days following study intervention discontinuation, all (S)AEs are collected, regardless of causality.

^d For anti-cancer therapies, also collect prior to 28 days.

e Treatment compliance will also be assessed at each visit when study intervention is dispensed.

f Bioelectrical impedance scale to be used.

⁹ To be collected and updated as needed, not visit dependent. Eligibility assessments need to be completed prior to the patient being enrolled to the study.

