2.2 Background

Prostate cancer is the second most common cancer in men worldwide, with an estimated incidence of 900,000 cases and 258,000 deaths in 2008 (Fizazi et al. 2020). In the United States, approximately 222,000 cases were diagnosed in 2010 (Jemal et al. 2011), of which an estimated two-thirds undergo radical prostatectomy or definitive radiation therapy (RT). Approximately 25%-35% of patients treated with definitive surgical or radiation therapy for localized adenocarcinoma of the prostate will recur in the form of rising serum PSA without overt metastatic disease, termed biochemical recurrence (BCR) (Jemal et al. 2010, Zietman et al. 2004). An estimated 40,000 - 50,000 men in the U.S. develop biochemically relapsed prostate cancer each year, yet treatment of men in this disease state is far from standardized. The optimal time to initiate treatment and the choice of specific therapy for such patients remains controversial and highly variable in clinical practice. This may be due to several potential reasons, including (1) absence of prospective randomized trial data demonstrating an overall survival advantage for one therapeutic approach and (2) a biologically heterogeneous population with a variable natural disease course.

Biochemical recurrence (BCR) of prostate cancer, characterized by a rising prostate-specific

Page: 27 of 86

antigen (PSA) after definitive primary therapy, occurs in approximately 20-40% of post-prostatectomy patients and 30-50% of post-radiation patients within 10 years (Artibani et al. 2018). While many patients with BCR do well clinically for years, proper treatment of BCR is important as BCR precedes the appearance of clinical metastasis by 8 years after radical prostatectomy (RP) and by 7 years after primary definitive RT (Artibani et al. 2018).

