5.1 Inclusion Criteria

- 1. Male of \geq 18 years of age.
- 2. Patients must have histologically or cytologically confirmed adenocarcinoma of the prostate.
- 3. Prior treatment with primary radical prostatectomy or definitive RT for localized prostate cancer.
- 4. Patients must have PSA ≥0.2 ng/mL after ART or SRT post-RP or after RP in participants who are unfit for ART or SRT, OR PSA ≥2 ng/mL above the nadir after primary RT only. (RP, radical prostatectomy; ART, adjuvant radiotherapy; SRT, salvage radiotherapy; RT primary radiotherapy)
- 5. The presence of < 5 asymptomatic (symptomatic lesions should be excluded) metastatic lesions (except for visceral metastases), and including extra-pelvic lymph nodes, and > 2 cm pelvic lymph nodes, on conventional or PSMA-PET based imaging methods is permitted. Lesions that need treatment with any opioid based analgetic are considered symptomatic.
- 6. PSADT ≤ 20 months calculated per PCWG3 + RECIST 1.1 per Scher et al. (Scher et al. 2016) and MSKCC nomogram.
- 7. ECOG PS of 0 1.
- 8. Serum testosterone >150 ng/dl.
- 9. Patients must have adequate organ function within 4 weeks before the first dose of study intervention and evidenced by:
 - a. Absolute Neutrophil Count $\geq 1500/\text{mm}^3$
 - b. Platelet count > 100,000/mm³
 - c. Total bilirubin < 1.5 x ULN
 - d. ALT and AST $\leq 1.5 \text{ x ULN}$
 - e. Creatinine < 2.0 X ULN
 - f. Creatinine clearance (CrCl) of ≥ 30 mL/min. CrCl should be calculated at screening using the Cockcroft-Gault formula: Creatinine clearance for males (mL/min) = (140 age in years) x (body weight in kg)/[72 x (serum creatinine in mg/dl)].
 - g. PTT, PT, INR \leq 1.5 x ULN (except if on the aprentic anticoagulation in which case the patient can be enrolled if stable and anti-coagulation levels are appropriate for their condition per good clinical practice).

NOTE: All values must be obtained within 4 weeks prior to first dose of darolutamide.

NOTE: Participants must not have received any growth factor within 4 weeks or a blood transfusion within 7 days prior to the hematology laboratory sample obtained at Screening.

- 10. Sexually active male participants must agree to use condoms as an effective barrier method and refrain from sperm donation, and/or their female partners of reproductive potential to use a method of effective birth control, during the treatment with study intervention and for 3 months after treatment with study intervention.

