		Section 4.1.3: Remove 'within +/- 7 days of scheduled date'	Account for baseline measures done outside the window		
		Section 4.1.3: Clarify the nearest measure prior to the study drug administration date will be used for baseline	To include the baseline measures recorded in the 'Unscheduled' visit CRF pages		
		Section 4.1.3: Revise the logic to choose the measurement for the analysis	Remove ambiguity around 'scheduled date' and to include 'unscheduled' pos baseline measurement incase scheduled visits do not exist		
		Section 4.2.1: Remove 'darolutamide' from the primary analysis timepoint for randomized phase	Align with protocol v2.0 that last participant could be on either arm in randomized phase		
		Section 4.3.1.1 Change 'absolute' PSA response to 'Undetectable' PSA response, and 50% and 90% 'relative' PSA response to PSA50, PSA90.	Align with terminologies commonly used in other literature		
		Section 4.3.1.1 Remove relative 30% PSA response (PSA30)	To focus on PSA50 and PSA90 since response rate in mHSPC is very high		
		Section 4.3.1.1 Add 0.2 ng/mL detection limit value to PSA response rates definitions	Clarify detection limit		
		Section 4.3.1.1 Add Breast enlargement, Breast	Summarize all AEs classified as feminizing side-effects		
		mass, Breast swelling in gynecomastia Section 4.3.1.1 Add analysis of AEs of special	Summarize common AEs associated		
		Section 4.3.1.2: Add 'and a Toeplitz covariance structure' to the SAS PROC MIXED details	with ARI treatment Align with protocol v2.0		

Page: 5 of 31

ARAMON V3.0

_	1		
		Section 4.5: Remove language related to	Laboratory measures are not graded in
		grading of laboratory measures	this study
		Section 4.5.2 Remove TEAEs with incidence of	Not meaningful with the sample size of
		at least 5% table	the study
		Section 4.5.2 Add drug related TEAEs; add a	Elaborate safety findings
		comprehensive list of safety tables planned	
		Section 4.6.1: Add free testosterone as	Explore the treatment effect of
		exploratory analysis for lead-in phase primary	darolutamide on free testosterone
		analysis	
		Section 4.6.1: Remove FACT-P and exploratory	Prioritizing the important endpoints for
		endpoints from lead-in primary analysis	decision making to go into the
			randomized phase
		Section 6.1.1: Add Discontinued from treatment	Align with clarification on active follow-
		along with the primary reason for discontinuation	up in protocol v2.0
		in place of participants continued after treatment	

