6.1.2 Demographics and baseline characteristics

Overall descriptive summaries of demographics and baseline characteristics will be presented for the lead-in phase, and by treatment arm as well for the randomized phase on the Evaluable population.

The following demographic data will be summarized:

- Age (years)
- Age category ($<65, 65-74, 75-84, \ge 85 \text{ years}$)
- Ethnicity
- Race
- Weight (kg)
- BMI (kg/m²)

The following baseline characteristics will be summarized:

- ECOG Performance Status
- Stage of prostate cancer at initial diagnosis
- Gleason score of prostate cancer (<8, \ge 8) at initial diagnosis
- Stage of prostate cancer at study entry
- Serum testosterone group ($< 150 \text{ ng/dL}, \ge 150 \text{ ng/dL}$)
- Time from initial diagnosis to first dose of study drug (months)
- Bone lesions at baseline (Y/N)
- Number of bone lesions at baseline
- Hepatic function at baseline:
 - o Normal: Total bilirubin and AST \leq upper limit of normal (ULN)

ARAMON V3.0

o Mild impairment: Total bilirubin > ULN to 1.5 x ULN or (Total bilirubin ≤ ULN and AST > ULN)

Page: 22 of 31

- o Moderate impairment: Total bilirubin > 1.5 to 3 x ULN, any AST
- Severe impairment: Total bilirubin > 3 x ULN, any AST.
- Estimated glomerular filtration rate (eGFR) at baseline:
 - o eGFR = $[(140 Age) \times Weight/(72 \times Creatinine)]$.

The following baseline lab values, assessed in secondary and exploratory endpoints, will be summarized in a separate baseline table:

- Serum testosterone
- Free testosterone
- PSA
- Sex hormones
- Fat and glucose metabolism
- FACT-P
- Bone turnover
- Physical function

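### Criterion 5 admits men with up to four metastatic lesions on conventional imaging, whom the protocol's own definition of biochemical recurrence excludes, so results reported as BCR may come from a mixed population

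*Protocol*

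**What the plan says.** **Definition.** Protocol 1.2 characterizes BCR as a rising PSA after curative treatment "without recurrent or metastatic cancer on conventional imaging studies". Section 2.2 gives the same idea without naming the imaging: "rising serum PSA without overt metastatic disease, termed biochemical recurrence (BCR".

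**Population.** Protocol 1.3, 4.1 and 5 and SAP 1.2.1 describe the men under study as hormone-naïve with BCR. The secondary safety objective of the lead-in phase reads "To assess safety of darolutamide monotherapy in patients with hormone-naïve prostate cancer with BCR" (Table 1-1). The safety and QoL objective of the randomized phase also names BCR (Table 1-2). Tables 3-1 and 3-2 and SAP 1.1 repeat both.

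**Eligibility.** Criterion 5 in Protocol 5.1 begins "The presence of < 5 asymptomatic (symptomatic lesions should be excluded) metastatic lesions (except for visceral metastases". It goes on to cover extra-pelvic nodes and pelvic nodes above 2 cm, and ends "on conventional or PSMA-PET based imaging methods is permitted". The imaging footnote to the Schedule of Activities says "Radiological tumor assessments will be conducted only at screening to exclude presence of visceral metastases".

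**Reporting.** SAP 6.1.2 lists "Bone lesions at baseline (Y/N", the number of bone lesions, and the stage of cancer at study entry. It lists neither nodal lesions nor the imaging method.

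**The concern.** The protocol defines its disease state by the absence of metastases and then admits men who have them. If such men enrol, the PSA response, safety and QoL summaries describe a blend of BCR and oligometastatic disease while carrying the label BCR. A reader who applies the results to men without metastases would not know how far they rest on such men.

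Bone turnover raises a more specific issue. BSAP and CTX are compared between arms in a model that pools men with and without bone metastases. Tumour in bone may itself influence these markers, and with about 20 men per arm a chance imbalance in bone lesions could be read as a drug effect on bone.

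**Working it through.** The plan gives no figure on this point, so the check is mainly a comparison of texts. Fewer than five lesions means 0 to 4.

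**1. Who is eligible, and who has BCR as defined?**

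| Finding at screening | Criterion 5 | BCR per 1.2 | BCR per 2.2 |
|---|---|---|---|
| No lesions | admitted | yes | yes |
| 1–4 asymptomatic non-visceral lesions, PSMA-PET only | admitted | yes | depends on the meaning of overt |
| 1–4 asymptomatic non-visceral lesions on conventional imaging | admitted | **no** | **no**, on a plain reading |
| Visceral or symptomatic lesions, or five or more | not admitted | – | – |

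The third row is the contradiction.

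**2. Does the protocol use BCR in a wider sense that includes metastases?** No. Section 1.2 says BCR comes 8 years (after prostatectomy) or 7 years (after radiotherapy) before clinical metastasis. It also describes the enzalutamide reference study as enrolling two groups, biochemically recurrent and metastatic.

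**3. Does any analysis separate these men?**
- The evaluable and safety sets (Protocol 9.3, SAP 3) take no account of lesion status beyond general eligibility.
- Protocol 6.3 names no stratification factor.
- The only planned subgroup (SAP 4.6.2) is by week-12 testosterone increase in the lead-in phase.
- Bone-turnover markers (SAP 4.4) follow the sex-hormone model. Its code in SAP Appendix 6 has treatment, visit and their interaction, with no baseline covariate.

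**4. Does the primary comparison depend on lesion status?** Not as planned. The sample-size inputs are mean percent changes of 45% and 110%, SDs of 65% and 75%, and 20 men per arm. None refers to lesions, and the documents give no reason to expect a different testosterone response in men with lesions.

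**5. How uneven could the arms be by chance?** The share of men with lesions is not given, so I assume K = 4, 8 or 12 of 40 randomized (10%, 20%, 30%). With X lesion-positive men in one arm of 20, X is hypergeometric and the between-arm difference is |2X − K|. For K = 4, a difference of 4 needs X = 0 or 4:

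P = 2 × C(20,4) / C(40,4) = 2 × 4,845 / 91,390 = 0.106.

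| K of 40 | P(difference of 4 or more men) |
|---|---|
| 4 | 0.106 |
| 8 | 0.235 |
| 12 | 0.301 |

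These probabilities apply to any unstratified factor of that frequency. They support a covariate in the bone-marker model. They do not measure the size of the definition mismatch.

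**The case against.** The best defence is that the breadth is deliberate. Criterion 5 is explicit, screening imaging is there to exclude visceral disease only, and the enzalutamide reference study was itself mixed. Section 2.2 also characterizes BCR a second time with no imaging clause. On this view, loose background wording meets a clear eligibility rule. That may well be the intent, and it would favour restating the population. It does not remove the conflict, because BCR remains the stated population in both documents.

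Several further points stand:
- The primary objective rows name no disease population, and the title says only hormone-naïve prostate cancer, which criterion 5 does not contradict. The design statements in 1.3 and 4.1 do tie the testosterone question to men with BCR.
- SAP 6.1.2 tabulates stage at study entry, so disease extent is not wholly unreported.
- BSAP and CTX are exploratory, and randomization balances bone lesions in expectation. The covariate protects against chance imbalance only.
- A PSA split on a handful of men would say little.

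A reader might also take the SAP version history, which drops the 30% PSA response "since response rate in mHSPC is very high", as proof that the sponsor regards the trial as metastatic. It is only the reason given for one endpoint change. It defines no population and is weak evidence.

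**Conclusion.** The contradiction is real, and nothing in either document resolves it. Men with one to four asymptomatic non-visceral metastases on conventional imaging are eligible but fall outside the protocol's definition of BCR, and no planned analysis distinguishes them. The analysed sets may be mixed in unknown proportion.

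Two stronger readings are tempting and are not supported. One is that the men analysed are not the stated population. Criterion 5 permits lesions without requiring them, and men with no lesions, or with lesions seen only on PSMA-PET, still meet the definition in 1.2. The other is that the trial cannot answer its question. No effect on the week-12 testosterone comparison, its power or its alpha is shown.

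The consequence is for how conclusions are worded and, secondarily, for the exploratory bone-marker comparison. Only the imbalance probabilities are numerical, and they rest on assumed shares of 10% to 30%.

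**What to change.** 1. Reconcile the BCR definition and population statements with criterion 5. Which of them governs is for the sponsor to decide.
2. If criterion 5 stands, restate the population as BCR by PSA, with or without fewer than five asymptomatic non-visceral metastases. Do this in Protocol 1.2, 1.3, 4.1 and 5, in the safety/QoL objectives (Tables 1-1, 1-2, 3-1, 3-2), and in SAP 1.1 and 1.2.1. Word conclusions to match.
3. Add bone lesions at baseline (Y/N) as a covariate in the BSAP/CTX model (SAP 4.4, with the code in Appendix 6). The item is already tabulated in SAP 6.1.2.
4. Optionally, show PSA response descriptively by lesion status, and add nodal lesions and imaging method to SAP 6.1.2 where captured. Capture needs checking first: PSMA-PET is optional and sites are only encouraged to enter its results.

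The cost is text changes, one degree of freedom in an exploratory model, small descriptive subgroups, and a conclusion worded for a broader population. With criterion 5 kept, recruitment is unaffected. The primary analysis does not change.

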1.3 Overall Design

[figure not shown]
This is a two-stage phase 2 open label study, with a lead-in phase and randomized phase to assess the impact of darolutamide or enzalutamide as a monotherapy treatment on serum testosterone levels in men with hormone-naïve prostate cancer experiencing biochemical recurrence (BCR) after failure of treatment with curative intent for localized prostate cancer. Secondary endpoints to be evaluated include the impact of darolutamide or enzalutamide monotherapy on energy metabolism and the metabolism of sex hormones as well as PSA response and safety.

Exploratory endpoints will evaluate changes in bone metabolism and physical function.

^{*}the physical function assessments might be modified.

Page: 17 of 86

Figure 1-1: Study Schema

Abbreviations: ECOG Eastern cooperative oncology group, PC prostate cancer, PSADT PSA doubling time.

Page: 18 of 86

1.4 Number of Participants:

During the lead-in phase 25 participants will be assigned in a single cohort to darolutamide to ensure that 20 participants treated with darolutamide for 12 weeks are evaluable for serum testosterone level at week 12.

The conduct of the randomized phase is dependent on the results of the lead-in phase. Further details follow later in the protocol. If the study proceeds into the randomized phase, it is planned that 40 patients (20 per arm) are enrolled in the randomized phase to have 34 evaluable participants for the final analysis. The projected number of total participants for this study is 65. Nevertheless, the sample size of the randomized phase might be adjusted according to the results obtained in the lead-in phase. Participants will only take part in one of the phases of the study.

1.4.1 Treatment Groups and Duration:

The treatments to be administered during the study:

In the lead-in phase participants will receive darolutamide 600 mg bid for a total duration of 52 weeks until unacceptable toxicity, PSA progression, withdrawal of consent, investigator's or patient's decision to stop therapy for the patient, Sponsor's decision to terminate the study, or death. The Sponsor withholds the right to conduct or stop the lead-in phase in case data on testosterone levels from patients treated with darolutamide alone would become available from other ongoing studies.

The conduct of the randomized phase is contingent on the results of the lead-in phase unless data from other ongoing studies could provide similar evidence. Participants will receive darolutamide 600 mg bid or enzalutamide 160 mg once daily for a total duration of 52 weeks until unacceptable toxicity, PSA progression, withdrawal of consent, investigator's or patient's decision to stop therapy, Sponsor's decision to terminate the study, or death. Following the 52-week intervention, all participants will be offered to continue the treatment with darolutamide as per investigator decision, including patients randomized to enzalutamide who would switch to treatment with darolutamide.

Page: 19 of 86

Study Intervention Lead-in phase

Study Intervention	Darolutamide
Dosage Level(s)	Darolutamide 600 mg (2 tablets of 300 mg) will be administered twice daily with food, equivalent to a total daily dose of 1200 mg
Route of Administration	Oral (p.o.)
Use	Experimental

Study Interventions Randomized phase

Study Intervention	Darolutamide
Dosage Level(s)	Darolutamide 600 mg (2 tablets of 300 mg) will be administered twice daily with food, equivalent to a total daily dose of 1200 mg
Route of Administration	Oral (p.o.)
Use	Experimental

Study Intervention	Enzalutamide
Dosage Level(s)	Enzalutamide 160 mg will be administered once daily with or without food
Route of Administration	Oral (p.o.)
Use	Experimental

The expected study duration for the lead-in phase is 18 months assuming 20 evaluable participants are enrolled within an enrollment period of 6 months and treated for 12 months (52 weeks). The expected study duration for the randomized phase is 25 months assuming 40 participants are enrolled within an enrollment period of 12 months. For each phase the primary analysis will be at 12 weeks. The final analysis for both phases will be conducted after all subjects have completed the 52 weeks of treatment and will analyze the long-term results of the secondary endpoints.

1.4.1.1 Lead-in phase:

).

During the lead-in phase 25 participants will be assigned in a single cohort to darolutamide to ensure that 20 participants treated with darolutamide for 12 weeks are evaluable for serum testosterone level at week 12. This sample size will help estimate the mean percent change in serum testosterone level from baseline at 12 weeks within at most +/- 25%, assuming a true mean percent increase of less than 45%. This assessment uses a log normal distribution for percent change.

The conduct of the randomized phase is binding to a condition of obtaining an estimated mean percent increase from baseline in serum testosterone level at 12 weeks of less than 45%, and non-binding to a condition that the incidence of feminizing side effects observed is below that previously reported (CC)

The Sponsor reserves the right to conduct or stop the lead-in phase in case data on testosterone levels from patients treated with darolutamide alone would become available from other ongoing studies.

Page: 20 of 86

1.4.1.2 Randomized phase:

A maximum of 40 participants (20 per arm) will be randomly assigned to study treatment (darolutamide or enzalutamide) such that approximately 34 evaluable participants complete the study. The randomized stage will require a sample size of 20 per group to provide 85% power to test the null hypothesis of no-difference between groups on mean percent change at two-sided 0.05 level. This assessment is based on a mean percent change in serum testosterone from baseline and Standard Deviation for the darolutamide arm of 45% and 65% versus 110% and 75% respectively for enzalutamide. The final sample size and time of testosterone assessments may be modified according to the results of the lead-in phase.

